### 3. TREATMENT OF SUBJECTS

#### 3.1 OPTIMA FORMA intervention

The core of GDM programme including person-centered and holistic approach is a cyclical process described in Figure 1. The practice nurse in the general practice will act as case manager. She/he can consult the general practitioner or other health providers when necessary. The first step in the intervention is assessing the integral health status of the patient (health across multiple domains, including physiological measurements and symptoms of disease), using a (preferably digital) questionnaire at home and physical measurements. The second step is an appointment in which the results are discussed with the patient in a semi-structured way. The case manager discusses if the results are recognizable, if there are other issues which haven't come up, and the priorities of the patient. Personal goals are formulated in the third step, which can range from purely medical goals to social goals. In the fourth step, the healthcare professional and patient will choose through shared-decision making the most appropriate interventions and support to achieve these goals. The goals and interventions are documented in a personal healthcare plan, which is preferably digitally available for all relevant healthcare professionals and the patient. Next, referrals are made if necessary and the treatment is started. An evaluation is planned and carried out, if necessary multiple times. If a treatment goal is reached or another treatment goal is more urgent, the cycle can be repeated.

[figure not shown]

Figure 1. Presentation of the cyclic process of the GDM programme

In order to provide the OPTIMA FORMA intervention to participating patients all healthcare professionals involved will be trained by their primary care cooperative on the concept of Positive Health, communication skills, use of materials and ICT, and interprofessional collaboration prior to the start of the intervention. During follow-up, the

practices will receive additional support from the primary care cooperative through intervision meetings and case report discussions.

### **3.2 Usual care**

Practices in the control group provide care as usual, which consists of the SDM programmes according to the national care standards and General Practice guidelines (NHG) for DM2, COPD and CVD. According to these protocolised programmes, patients with COPD, CVD or DM2 visit their general practice at a standard frequency per year (1 – 4 times) and standard monitoring measurements and topics are discussed.

The practices that are randomised to the control group will not receive any additional training related to this study.

## **4. METHODS**

### **4.1 Study parameters/endpoints**

Outcome measurement will be based on the quadruple aim framework.[16] To measure population health we will assess quality of life, self-management, and disease-specific physiological factors. Our composite primary outcome will be health-related quality of life *and* patient experience, measured with the PROMIS Global 10 and P3CEQ, as described in paragraph 2.4. Secondary outcomes will be: self-management, measured with the Dutch short version of the patient activation measure (PAM-13).[17] Measurement of disease-specific physiological factors will take place as part of routine care in both study groups and include blood pressure, body mass index (BMI), cholesterol, blood glucose levels and lung function parameters, if applicable. All outcomes will be measured at baseline, 6 months, and 12 months follow-up. Physiological factors will be recorded in the electronic medical records as part of routine care and will be extracted from 3 months before baseline until 12 months follow-up. Also, healthcare utilisation and prescription data will be extracted from the electronic medical records at the end of follow-up. Health care provider experiences will be measured with an appropriate self-reported experience measure.

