Because we value each aim (population health and patient experience) as equally important, we are using a composite primary outcome, which consist of the percentage of patients who have a clinically relevant improvement of at least the minimal clinically important difference (MCID), defined as  $0.5 \times \text{SD}$  of the baseline mean, in either the PROMIS GMH score OR the PROMIS GPH score OR the P3CEQ-score AND who experience no decrease of at least the MCID in either the PROMIS GMH score OR the PROMIS GPH score OR the P3CEQ-score.

In our recent pilot study [unpublished] we followed 98 patients who received our intervention for six months. Of the 79 patients who completed all questionnaires, we found that in 30.4% of the patients the requirements for a positive score on the composite primary outcome were met. Loss to follow-up was 20%. Based on these results and the longer duration of intervention in the evaluation study (12 months vs 6 months), we hypothesised that in the evaluation study 35% of the intervention patients compared to 20% of the usual care patients will improve more than  $0.5 \times$  the expected SD of baseline mean on one of the scores at 12 months, and show no decrease of the MCID on the other scores. We estimate that we need a total sample size of 680 patients (17 practices with an average of 40 patients per practice) to detect a difference of 15% between the control and intervention group, taken into account an alpha level of 5%, a power of 80%, an intra-class correlation coefficient (ICC) of 0.03 [15], and a loss to follow-up of 20%.

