#### **4.1.2 Secondary study parameters/endpoints (if applicable)**

- PROMIS dimension GPH score
- PROMIS dimension GPM score
- P3CEQ-score

- Patient Activation Measure (PAM)
- EQ-5D-5L
- Health care use according to Medical Consumption Questionnaire
- Health care use according to general practice data
- Body weight, BMI, smoking status, HbA1c, glucose, cholesterol levels and blood pressure from general practice data (registered for normal care).
- Experience of healthcare providers on COPILOT and MAS-GZ questionnaire

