### 6. STATISTICAL ANALYSIS

Data analysis will be performed according to the intention-to-treat principle. Data from patients who discontinued follow-up will be included in the analysis up to the point of dropout. Descriptive analyses will be performed to describe the patient characteristics. Mean and standard deviation (std) or median and interquartile range for continuous characteristics and number and percentages for categorical characteristics will be determined. The relationship between treatment and outcome measures measured at 6 and 12 month follow up will be analysed with mixed three level linear or logistic regression, taking into account that the times of measurement (after 6 and 12 months) are clustered within patients, and patients within general practices. We will perform a

model with a random intercept and all other variables fixed. To test the effect of the intervention a model with time, group (intervention or control) and the interaction between time and group will be performed. Covariates included in the analyses will be age, sex, smoking status, education level, and social support. A value of  $p < 0.05$  will be considered statistically significant for all analyses, based on two-sided testing. Analyses will be performed using the Statistical Package for Social Sciences (SPSS, IBM Corp., Armonk, NY) version 25.

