### **6.2 Secondary study parameter(s)**

The relationship between treatment and secondary outcome measures measured at 6 and 12 month follow up will be analysed with mixed three level linear or logistic regression, taking into account that the times of measurement (after 6 and 12 months) are clustered within patients, and patients within general practices. A model with time, group (intervention or control) and the interaction between time and group will be performed. Covariates included in the analyses will be age, sex, smoking status, education level, and social support

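### HbA1c, glucose and cholesterol are called disease-specific, but the plan sets no disease-based analysis population and no programme covariate for them

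*Combined protocol and SAP*

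**What the plan says.** Section 4.1 introduces the physiological outcomes with "Measurement of disease-specific physiological factors will take place as part of routine care in both study groups". It lists blood pressure, BMI, cholesterol, blood glucose and lung function, with a closing qualifier that limits them to where they apply. The qualifier is not turned into an analysis population.

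Section 4.1.2 repeats most of these as secondary endpoints, including "HbA1c, glucose, cholesterol levels and blood pressure from general practice data (registered for normal care", with no restriction by disease. Lung function is absent from that list.

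Sections 2.1 and 2.2 admit anyone enrolled in a DM2, COPD, asthma or CVD programme, with no quota per disease. Section 4.2 stratifies randomisation by cooperative and by the socioeconomic status of the practice population, not by disease.

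Section 6.2 gives one model for every secondary outcome: time, group and their interaction, with measurements nested in patients and patients in practices. On adjustment it says "Covariates included in the analyses will be age, sex, smoking status, education level, and social support". Neither programme nor baseline value is named.

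On how values arise, section 3.1 starts the intervention by "assessing the integral health status of the patient (health across multiple domains, including physiological measurements and symptoms of disease". Under section 3.2, controls attend at a standard frequency under single-disease protocols, and "standard monitoring measurements and topics are discussed".

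**The concern.** A measure such as HbA1c has a clear target population, the patients with diabetes. If the comparison takes in every patient with a recorded value, two things follow.

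First, an effect that can occur only in patients with the disease is averaged with patients in whom it cannot occur. The estimate shrinks and the variance grows.

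Second, mean level depends on the disease mix of those measured. Randomisation balances enrolment up to chance. It does not fix who has a value recorded during follow-up, because that depends on the care given. If one arm records glucose or HbA1c in more patients without diabetes, its mean falls although no patient has changed.

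Leaving the population open also leaves a choice, after results are seen, between analysing everyone with a value and analysing the index disease only.

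**Working it through.** **1. The plan's own figure.** The only sample-size figure, 680 patients (17 practices of 40), is for the primary composite: "35% of the intervention patients compared to 20% of the usual care patients", 5% alpha, 80% power, ICC 0.03, 20% loss. Two-sided with 1:1 allocation this gives 138 per arm, 276 in total. With 40 × 0.8 = 32 completers per practice, the design effect is 1 + 31 × 0.03 = 1.93. Then 276 × 1.93 / 0.8 = 666, or 16.6 practices, rounded up to 17. The figure reproduces, but it says nothing about physiological outcomes. The documents give no SD, effect, ICC, disease share or recording rate for these, so steps 2 to 5 illustrate mechanisms under stated assumptions.

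**2. Dilution.** If every patient has a value and only those with the disease can respond, pooled effect = disease share × true effect. Assumed shares of 30%, 50%, 70% and 90% leave 0.3, 0.5, 0.7 and 0.9 of the effect.

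Now assume 50% are in the DM2 programme, all of them measured; a fraction q of the others measured equally in both arms; a mean gap g between DM2 and other patients of 1.0 to 1.5 within-disease SD; ICC 0.03; and 32 patients per practice.
- DM2 share among those measured: s = 0.5 / (0.5 + 0.5q).
- Pooled variance: 1 + s(1 − s)g². Measured per practice: m = 32(0.5 + 0.5q). Design effect: 1 + (m − 1) × 0.03.
- DM2-only analysis: 16 per practice, design effect 1.45, signal proportional to 1/√(1.45/16) = 3.32.
- q = 0.2, g = 1.0: s = 0.833, m = 19.2, signal 0.833/√(1.139 × 1.546/19.2) = 2.75, ratio 0.83.
- q = 1.0, g = 1.5: s = 0.5, m = 32, signal 0.5/√(1.5625 × 1.93/32) = 1.63, ratio 0.49.

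The pooled analysis keeps 49% to 83% of the signal-to-noise ratio of the DM2-only analysis, despite its larger numbers.

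**3. Chance differences in mix.** Assume a 50% share, 40 patients per practice and an ICC of disease share of 0.01 to 0.10. The SD of the between-arm difference in share is √[0.25 × (1 + 39 × ICC) × (1/n₁ + 1/n₂)].
- 10 v 5 practices (400 v 200 patients): 0.051 to 0.096.
- 10 v 10 practices, if the five extra control practices in section 4.2 are all used: 0.042 to 0.078.

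Differences of 5 to 10 percentage points are therefore ordinary. With an assumed HbA1c gap of 10 to 14 mmol/mol, they shift the level by 0.5 to 0.7 (5 points) or 1.0 to 1.4 mmol/mol (10 points). On average this is noise, not bias, but a programme covariate would remove much of it.

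**4. Different recording by arm.** Use the assumptions of step 2, with no true effect. With 20% of non-DM2 patients measured in one arm, s = 0.833. With 30%, 40% or 60% in the other, s = 0.769, 0.714 or 0.625. The spurious difference in level is the difference in share × g:
- 20% v 30%: 0.064 × (1.0 to 1.5) = 0.06 to 0.10 SD.
- 20% v 40%: 0.119 × (1.0 to 1.5) = 0.12 to 0.18 SD.
- 20% v 60%: 0.208 × (1.0 to 1.5) = 0.21 to 0.31 SD.
- Equal recording: zero.

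The arm that records more non-DM2 patients looks better. The documents do not say which arm that would be.

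**5. Baseline values.** Step 4 uses follow-up levels only. I simulated a time-by-group model with baseline as a time level and a random patient intercept. It assumed 20% non-DM2 recording in both arms at baseline and a within-patient correlation of 0.5 to 0.7. The 0.12 to 0.31 SD fell to roughly 0 to 0.08 SD. Whether baseline enters is unclear. The summary speaks of comparing changes, and section 4.1 has all outcomes measured at baseline. Section 6 models the 6- and 12-month values without naming a baseline term, and the table in 4.3 lists physiological parameters at 12 months only.

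**The case against.** A reader might infer that the plan does compare these outcomes over every patient with a value. The documents do not say so. Section 4.1 calls the factors disease-specific and limits them to where they apply, and 4.1.2 is a short list under the same heading. Restriction by disease may well be intended. What stands is that neither 4.1.2 nor 6.2 states it.

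A reader might also infer that recording differs by arm by design and favours the intervention. Section 4.1 says measurement is routine care in both groups. Section 3.1 mentions physiological measurements but names no blood test, and 3.2 does not list what each control protocol measures. Differential recording is plausible, not shown, and could run either way.

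The step 4 differences could be turned into false-positive rates: 7% to 10% at 20% v 30% recording, and 11% to 58% at 20% v 40% to 60%. Those rates rest wholly on assumed shares, gaps and recording, and on ignoring baseline. They should not be read as properties of this trial.

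Finally, blood pressure, weight and BMI are not tied to one disease, and dilution needs both pooling and an effect confined to one disease. Both points are right and narrow the concern to a few outcomes.

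**Conclusion.** The concern holds as a gap in the analysis specification. Outcomes labelled disease-specific have no disease-based analysis set, the one generic model has no programme term, and patients come from four programmes. Taken literally, the model runs on whoever has a value. Dilution then follows for any effect confined to one disease, in proportion to that disease's share among those measured. Disease mix can also move the comparison, by chance or through recording.

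The size and direction of any bias cannot be derived from the documents. The illustrations range from zero with equal recording to about 0.3 SD under strong assumptions with baseline ignored, and much less with baseline used. The primary composite is not affected. This is a worthwhile, inexpensive improvement to some secondary analyses, not a threat to the trial's main conclusion.

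**What to change.** In 4.1.2 and 6.2, state the analysis set of each physiological outcome by programme enrolment at baseline:
- HbA1c and glucose: patients in the DM2 programme.
- Cholesterol: patients in the DM2 or CVD programme.
- Lung function, if kept (4.1 lists it, 4.1.2 does not): patients in the COPD or asthma programme.
- Blood pressure, weight and BMI: all patients, with indicators for baseline programme (DM2, COPD, asthma, CVD) in the model.

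Include the baseline value where recorded, say how it enters the model, and align 4.1, 4.3 and section 6 on the time points. Report by arm how many patients in each set have a value.

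The cost is a few lines of text. Programme enrolment is the inclusion criterion, so it is known for every patient before follow-up. The downside is fewer patients for some outcomes. If restriction by disease was always intended, the change only writes it down.

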## 2. STUDY DESIGN

We will perform a cluster randomized controlled trial with a follow-up time of 12 months.

The three participating primary care cooperatives, i.e. Nijmegen, Arnhem, and Doetinchem, will recruit 15 general practices (clusters) who will be randomized using a 2:1 ratio in two study groups:

1. The intervention group: the GDM programme including a person-centered, integrated, and holistic approach
2. The control group: care as usual according the current SDM programmes

All practices will receive instructions from the research team on the procedures of the evaluation study. Participating practices will then start recruiting patients from a random sample of eligible patients, i.e. patients with DM2, COPD, or CVD who are currently receiving SDM. After written informed consent, information will be collected through questionnaires at baseline, 6 months and 12 months, and by interviews and data collection from electronic medical records. Information will also be collected from the participating healthcare providers through questionnaires and interviews.

In the two months prior to the start of the intervention, all practices in the intervention group will be trained in providing GDM by their own primary care cooperative. During follow-up two to three intervention meetings will take place including peer coaching and case study discussions.

Practices who are allocated to the usual care group will not receive any training, but will continue with their SDM programmes.

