## 2.2 Inclusion criteria

- Currently enrolled in any of the SDM programmes for DM2, COPD, asthma or CVD.

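### The 3-month look-back for physiological values is too short for patients seen one to three times a year, so many would lack the baseline value that Section 4.1 promises

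*Combined protocol and SAP*

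**What the plan says.** On timing, Section 4.1 states: "All outcomes will be measured at baseline, 6 months, and 12 months follow-up". On source, it states: "Measurement of disease-specific physiological factors will take place as part of routine care in both study groups". These values "will be extracted from 3 months before baseline until 12 months follow-up". No study measurement visit is scheduled at baseline.

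Under usual care (Section 3.2), patients "visit their general practice at a standard frequency per year (1 – 4 times) and standard monitoring measurements and topics are discussed". Section 2.2 admits only patients "Currently enrolled in any of the SDM programmes for DM2, COPD, asthma or CVD", so this visit pattern describes both arms before baseline.

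Enrolment is not linked to a review visit. Section 2 states: "Participating practices will then start recruiting patients from a random sample of eligible patients". Section 7.2 has the practice nurse invite them by phone or e-mail.

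Section 4.1.2 lists weight, BMI, HbA1c, glucose, cholesterol and blood pressure from practice records as secondary endpoints. The population-health table in Section 4.3 gives one time for physiological parameters, 12 months. No section says which record counts as the baseline value or what to do when there is none.

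**The concern.** Section 4.1 promises a baseline value but provides no measurement that guarantees one. Whether a patient has one depends on whether a routine visit happened to fall in the quarter before enrolment. For a patient reviewed once a year, it usually will not have.

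Without a baseline value, a patient cannot contribute to a change score or to the description of the groups at entry, and the model cannot use that patient's own starting level to reduce residual variance. The Summary frames effectiveness as a comparison of changes between groups, and Section 4.1 names physiological factors as part of population health, so baseline values are likely to be wanted.

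The absence of a baseline rule leaves a second opening. Extraction continues after baseline, so an analyst could fill the gap with the first later record. In the intervention arm, care begins with an assessment "using a (preferably digital) questionnaire at home and physical measurements", and Section 7.2 releases the patient to the new care only after the baseline questionnaire is completed. Enrolment triggers no such assessment in controls. A substitute value would therefore be taken after randomisation and timed differently by arm.

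**Working it through.** The documents give no coverage or missing-data figure for the physiological values, so there is none to reproduce.

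**Inputs**
- Look-back w = 3 months (Section 4.1).
- Routine visits k = 1, 2, 3 or 4 a year (Section 3.2). The share of patients at each frequency is not given.
- Assumption: the baseline date is unrelated to the date of the last routine visit. The random sample (Section 2) and the remote invitation (Section 7.2) support this but do not state it.

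**Formulas for the share with no visit in the look-back**
- Evenly spaced visits: 1 − min(1, k × w/12). For w = 3: 1 − 0.25 = 75%; 1 − 0.50 = 50%; 1 − 0.75 = 25%; 1 − 1 = 0%.
- Visits at random times (Poisson): exp(−k × w/12). For w = 3 and k = 1: exp(−0.25) = 78%.
- Simulation (20,000 replicates per case): visits 12/k months apart, each shifted by up to 1 month either way.

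| Visits a year | Evenly spaced | ±1 month shift | Poisson |
|---|---|---|---|
| 1 | 75% | 75% | 78% |
| 2 | 50% | 50% | 61% |
| 3 | 25% | 26% | 47% |
| 4 | 0% | 11% | 37% |

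**Overall share, evenly spaced visits, for assumed mixes**
- All seen once a year: 75%.
- The four frequencies equally common: (75 + 50 + 25 + 0)/4 = 37.5%.
- All seen four times a year: 0%.

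**Longer look-back: share of once-a-year patients who do have a value**

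| Look-back | Evenly spaced | ±1 month shift | Poisson |
|---|---|---|---|
| 3 months | 25% | 25% | 22% |
| 6 months | 50% | 50% | 39% |
| 12 months | 100% | 97% | 63% |

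**Does the written analysis drop these patients?** Sections 6 and 6.2 model the outcomes at 6 and 12 months on time, group and their interaction, with five patient characteristics as covariates. None of the five is a physiological measurement. A patient with a follow-up value but no baseline value therefore stays in the model.

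**The case against.** The strongest reply is that the planned secondary models do not need a baseline value. Randomised groups can be compared on follow-up values alone, and the Summary's sentence on comparing changes goes on to list questionnaires and cost data, not physiological values. This stands against any claim that the planned comparison is invalid. It does not remove the conflict within Section 4.1, which promises a baseline measurement, or the precision forgone.

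The size is also uncertain. The visit mix is unknown, and patients in more than one programme may be seen more often. In the other direction, a visit need not include every measurement, so coverage for a given measure could be lower than visit coverage. The honest overall range is 0% to 75%.

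The length of the look-back is a trade between coverage and recency. With evenly spaced yearly visits, a 12-month window yields values 0 to 12 months old, about 6 months on average. That is a real cost, although an older pre-intervention value is still usable as a covariate.

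A reader might infer three stronger points that the documents do not support:
- *That the baseline gap differs by arm.* All patients are in the single-disease programmes at entry, so look-back coverage should be similar. A difference would arise only if post-baseline records were used as substitutes, and the plan neither proposes nor excludes that.
- *That patients with a baseline value are the sicker ones.* Section 3.2 describes a standard visit frequency and does not link it to severity.
- *That most of the trial's patients will lack a baseline value.* This follows for once-a-year patients only, and their share is not given.

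**Conclusion.** The point holds as a gap in the plan for secondary endpoints. About three in four once-a-year patients (75% to 78% across the visit patterns tried) and at least half of twice-a-year patients (50% to 61%) would have no physiological value in the look-back. Over the whole trial the share is 0% to 75% with evenly spaced visits, and 37.5% under an equal mix.

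This rests on enrolment being unrelated to visit timing. For once-a-year patients, the word most would fail only if more than half of their visits fell in the 3 months before baseline.

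The loss is in baseline description, change scores and the precision available from baseline adjustment. The primary composite is built from questionnaires and is unaffected. The documents do not show bias in the secondary comparison as written. The risk of an arm difference is conditional on how missing baselines are filled, which is why the rule should be written down before extraction.

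**What to change.** 1. In Section 4.1, extend the extraction window to 12 months before baseline.
2. Define the baseline value, identically in both arms, as the last recorded value on or before the date of the baseline questionnaire. State that no value recorded after the intervention starts may serve as baseline.
3. In Section 6.2, add this value as a covariate in each secondary physiological model. Name a method for missing baselines that keeps every patient in the analysis.
4. Reconcile Section 4.1 (baseline, 6 and 12 months) with the Section 4.3 table (12 months only), and say which record counts for each time point. The longer look-back does not solve the related problem that a patient seen once a year cannot supply separate 6- and 12-month values.

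The cost is one changed date in the record query and a few sentences of text. The consent wording must cover the longer look-back. Some baseline values will be up to a year old, and coverage of once-a-year patients will fall short of 100% if visits are irregular (97% with a 1-month shift, 63% if visits are fully random). No visit or measurement is added for patients.
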